### *Progress Review*

All stakeholders will convene twice a year (month 7 and 12) and review the progress, issues, problems and feedback from the clinic sites, satisfaction survey and interim and final outcomes data. When necessary, changes to the protocol or interventions will occur if deemed appropriate by the group.

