### *Technology Design*

**Media:** A URL based app will be developed and tested. After each testing, notes will be taken by the SC and then reviewed by the team for clarity, flow, interest, and ease of use. NCCC and LCC will be asked to review and give feedback. Ten women will then be asked individually to review the URL and give feedback in a one to one setting. The URL website allows us to easily make changes over time as input is given.

**Userface design:** The media will be a combination of pictures, words, short videos and interactive buttons in order to engage and hold the attention of the woman.

The application will be developed using a responsive design approach—a website optimized for viewing on a tablet or phone allowing the app to be used on both iOS and Android devices as well as easily distributed later. The responsive design approach will allow the incorporation of videos and animation using HTML 5. During the study, the app will be distributed to clinics through a URL: <http://medschool2.ucsf.edu/preview/dots/site/>.

The application will be both unit and functionally tested to work in the targeted tablet devices and browsers identified by the study team. In addition, the study team will work with the identified clinics to ensure wireless coverage.

The tablet will not be set up to collect any data on individuals.

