### Missing Data

Missing data may arise at several points in the study. Clinicians have six months to submit a claim for reimbursement after the last date of service. The claims data are 90% complete at the last date of service and 99% after six months of the last date of service. We will feel confident that we can conduct the statistical analysis in years 1 (pre-intervention) and 3 (post-intervention) with a 90% complete dataset but will rerun the models in year 2 (interim data analysis) to confirm the results with the 99% complete dataset for pre-intervention and will rerun the end of study results at 6 months post end of study. Patient information may be missing on the examination or intake form or from the patient satisfaction survey or patients may drop out or be lost to follow-up in the study. The randomness of this information will be examined to ensure that its missing-ness is not related to any patient, clinic, or intervention arm factors. In addition to this, lab results may be contaminated or lost entirely. The pattern of unusable lab results will be analyzed to identify any clinic or intervention arm bias. Reasons for missing data will be collected and tabulated.

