**a) Decrease the rate of cervical cytology testing among women ages 21-29 years of age**

**Pre:** Rate of women 21-29 years of age who received cervical cytology tests over total number of women 21-29 years of age in quarter (3 months) before start of intervention

**Post:** Rate of women 21-29 years of age who received cervical cytology tests over total number of women 21-29 years of age in months 3-6, 9-12, and 15-18 after intervention started

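### The stakeholder group that reviews interim outcomes data during follow-up may also change the protocol or the interventions, with no limit on what it sees or alters

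*Combined protocol and SAP*

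**What the plan says.** Under Progress Review, all stakeholders meet twice a year, at months 7 and 12. They are to "review the progress, issues, problems and feedback from the clinic sites, satisfaction survey and interim and final outcomes data". The next sentence reads: "When necessary, changes to the protocol or interventions will occur if deemed appropriate by the group". The group's own judgement is the only criterion given.

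Under Data Analyses, the primary outcome (cytology testing rate) is measured in the quarter before the start and "in months 3-6, 9-12, and 15-18 after intervention started". The colposcopy and LEEP/cryotherapy rates use the same post windows. The test-interval outcome counts second tests 3 to 15 months after the start.

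Other sections point towards a settled intervention. Final Product Development has the patient website edited until the team and stakeholders agree on all content. The end of Final Pilot Testing has the product approved by several stakeholder bodies and all investigators. Benefits to Subjects sends the final intervention to both review boards before the randomised trial begins. None of these says that content is frozen afterwards.

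**The concern.** The people who see outcomes data and the people who may change the trial are the same group, and that group is not independent of the result. The Project Summary lists the stakeholders as contributors to the development of the interventions, and one stakeholder society designed the provider app. The plan describes no separation of outcome data from this group, no limit to technical repairs, no freeze of endpoints or content, and no analysis by intervention version.

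Two things are at stake. First, if content changes between windows, the post windows no longer estimate the effect of one intervention, and the report could not say which version the result belongs to. Second, the permission extends to the protocol, which contains the endpoint and window definitions. A change to those after outcomes have been seen would no longer be prespecified.

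**Working it through.** The plan gives no figure to reproduce on this point. The check sets the sections side by side; the arithmetic covers timing and two illustrations.

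**1. Do meetings fall between the windows?** The origin of months 7 and 12 is not stated, so both readings are tried, assuming that meetings continue through follow-up.

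- Counted from intervention start: month 7 lies after the first window (ends month 6) and before the second (starts month 9). Month 12 lies at the end of the second and before the third (starts month 15).
- Counted as months of each project year: meetings fall at 7, 12, 19, 24 and so on, so gaps alternate between 12 − 7 = 5 and 19 − 12 = 7 months. The stretch from month 6 to month 15 after start is 15 − 6 = 9 months. As 9 exceeds the longest gap of 7, at least one meeting falls in it.

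Missing Data puts claims at 90% complete at the last date of service, so data from the first window could be available at such a meeting.

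**2. Which comparison would a change affect?** Only the two intervention arms are randomised (Study Design, Overview); the comparison clinics are selected separately. The provider app is common to both randomised arms, while the patient tool is in one. An edit to the patient tool therefore changes one side of APP vs APP+PCA. Technology Design says the tool reaches clinics through a URL, so one central edit could reach all clinics in that arm. The Adherence paragraph says viewing data will not be site-specific, so exposure to each version could not be traced by clinic.

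**3. What would the estimate mean?** Assume, for illustration only, an effect of 5 points before a content change and 16 after, and an average over three windows (the plan does not say how the windows are combined).

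- Change before the second window: (5 + 16 + 16)/3 = 37/3 = 12.3 points.
- Change before the third window: (5 + 5 + 16)/3 = 26/3 = 8.7 points.

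Neither average describes either version. For the test-interval outcome, a change anywhere in months 3 to 15 falls inside its single period.

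**4. Is type I error affected?** If no version works, changing only the content leaves the null hypothesis true in every window, so the error rate is not inflated. Choosing the decisive window after seeing results is different. The 1% level in the sample size section is explained only by the two comparisons with control, and the primary analysis names no primary window. As an illustration, clinic-level t-tests were simulated with 7 clinics per arm, a shared control, 1% two-sided (sidedness assumed) and 100,000 runs. Between-window correlation was assumed to range from 0.9 to 0.

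| | One fixed window | Best of three windows |
|---|---|---|
| Per comparison | 1% | 2.0% to 3.0% |
| Either comparison | 1.9% | 3.7% to 5.6% |

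The bound for six independent tests is 1 − 0.99^6 = 5.85%. These figures apply only if the window were chosen on the results, which the plan does not propose.

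**The case against.** The strongest reply is that the plan intends a finished, approved intervention and that several stronger readings go too far. Much of this stands.

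- **That stakeholders will act on unblinded results.** A reader might infer this. The text does not say that results are shown by arm, and it permits changes without planning any. Equally, it describes no blinding and no pooled display.
- **That the year-2 run is a look at post-intervention results.** It is not described as one. Missing Data says the team "will rerun the models in year 2 (interim data analysis) to confirm the results with the 99% complete dataset for pre-intervention", which is a rerun of baseline data, and the post-intervention analysis is placed in year 3. The concern rests on Progress Review alone, which lists interim outcomes data without defining them.
- **That mid-trial editing of the website is planned.** The sentence "The URL website allows us to easily make changes over time as input is given" belongs to development, where the input is testers' feedback. It shows only that editing is technically easy.
- **That the error rate is inflated.** A content change alone does not do this, as shown above. Outcomes come from claims, so ascertainment would not be affected either.
- **That the randomised contrast is secondary here.** The primary tests are against the comparison group, and the plan says it is not powered for APP vs APP+PCA. That limits the weight of this contrast, but a content change would equally blur the comparison of APP+PCA with the comparison clinics.

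The approval steps before launch do not answer the point. They do not bar later changes, and Progress Review expressly allows them.

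**Conclusion.** The concern holds as a matter of trial conduct. The plan gives one group both interim outcomes data and authority to change the interventions or the protocol, at meetings at least one of which falls between the first and last post windows. Progress Review also needs to be reconciled with the sections that call for a final, approved intervention before the randomised trial.

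The main harm is to interpretation. In the worst case, a change straight after the first window, two of the three windows would reflect a modified intervention. Prespecification is lost only if an endpoint or window is changed after outcomes are seen. The size of either effect depends on a change that has not been made and cannot be computed from the documents; the illustrations rest on assumed effects and correlations. The conclusion on timing assumes that meetings continue at the stated months throughout follow-up. The amendment should be made, but this is not evidence that any result is already biased.

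**What to change.** Amend Progress Review as follows.

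1. Limit the mid-trial stakeholder review to process data: tablet function, refusals, site feedback and satisfaction. Quality Assurance and Satisfaction Survey already provide for collecting these.
2. Keep outcome data by arm with the biostatistical group until the last post window closes.
3. Fix the endpoint and window definitions and the content of both interventions from first site start.
4. Allow only technical repairs and corrections required by a change in national guidelines, each dated, applied to all affected clinics and reported.
5. If a content change does occur, keep the planned analysis as the main one and add a sensitivity analysis by intervention version, before and after the change date. Making only the pre-change windows the main analysis is not advised, since it could leave months 3 to 6 alone.

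The cost is a short amendment. Stakeholders lose the freedom to improve content mid-trial on the basis of outcomes; their input before launch and their feedback on usability are untouched. With seven clinics per arm, the analysis by version would be imprecise and should be reported as descriptive.

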### **Sample Size Estimates and Power Calculations**

The database for FY 2010/11 shows that 386 clinics fit the criteria with 89 sites available for arms 1-2 and 297 available for the comparison group. The mean number of female clients aged 21-29 years seen at the eligible clinics was 560 and the mean number of cytology specimens, colposcopic examinations and LEEP/cryoprocures for this age group was 297, 40, and 4, respectively. In 2012, the mean cytology interval was 19 months. Very few clinics had an interval >30 months. There were no differences for any of the above variables between those

sites eligible for intervention and those for comparison. These numbers have not changed significantly in the past 2 years and will be updated for the baseline assessment.

After enrolling 7 sites into each arm, we estimate that we would have approximately 2800-3500 women aged 21-29 years in each arm. For each arm, baseline cytology rate in this age group would be approximately 50%, rate of colposcopy procedures for those who had cytology would be 13%, and rate of LEEP/cryotherapy procedures for those referred to colposcopy would be 10%.

Sample size calculations for the primary endpoint (rate of cytology testing) are based on a pairwise comparison of observed changes from baseline in clinic-specific three-month testing rates between intervention study arms (APP or APP+PCA) and the control arm, using a t-test adjusted for clustering on the clinic level. The baseline rate in control clinics is assumed to be approximately 50%, consistent with the preliminary data presented above. Assuming that there will be no observed change in rates for control clinics during the testing period, our expected sample size of 9030 (i.e. 3010 per arm, seven clinics per arm, and an average of 430 women per clinic) will be sufficient to provide 90% power to detect a between-arm difference as small as 16% as significant. This calculation assumes a quite conservative value for the intracluster correlation of outcomes within clinics of 0.07, and is based on a 1% significance level to account for the fact that there will be two pairwise comparisons with the control arm (i.e. one per intervention arm). Accounting for as much as 10% missing data on testing rates, we will still retain more than 90% power to detect differences of this magnitude or larger between arms as significant at the 5% level. We should also retain adequate power to conduct additional sensitivity analyses investigating the possible confounding influence of clinic-level descriptors (e.g. race/ethnicity and age distribution) on observed results. Finally, we note that our proposed analysis that will account for within-clinic paired observation of outcome rates and adjust for baseline covariates will likely yield more power than the conservative estimates made above. Although the study is not powered to detect significant differences between intervention groups, a similar calculation for the comparison between the APP and APP+PCA groups indicates that we retain at least 70% power to detect a difference in observed changes in testing rates as small as 15% as significant at the 5% level.

Parallel calculations for the secondary colposcopy outcome also are based on between-arm comparison of changes in three-month colposcopy rates from baseline levels, and assume that approximately 50% of women will receive cytology at baseline and follow-up in the control group, and that colposcopy rates will also remain unchanged at 13%. We also assume that the intervention-related reduction in cytology will result in approximately 20% fewer women eligible for colposcopy at follow-up. Based on similar assumptions about intracluster correlation and loss to follow-up, results indicate that with the planned total sample size of 9030, we will retain at least 80% power to detect an intervention-related reduction in colposcopy rate as small as 8% at the 5% (one-sided) significance level. Due to our conservative assumptions, we should have sufficient power to detect even smaller intervention-related effects in analyses adjusting for baseline characteristics.

We did not perform calculations for the testing interval length and LEEP outcomes because of the lack of preliminary data on their potential variability within and between clinics.

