## **PROJECT SUMMARY**

**BACKGROUND** Screening with cytology has accompanied large decreases in cervical cancer mortality in the US. However, cytology remains a relatively non-specific test resulting in needless invasive procedures for many women. Studies show that young women are specifically vulnerable since over-screening results in overtreatment with excisional therapies that have been associated with premature delivery and emotional distress. Current national guidelines recommend that routine screening be performed at less-frequent intervals and excisional cervical therapies are discouraged in young women. Uptake of these guidelines has been low for several reasons: many women expect annual cytology, physicians may have financial incentives and/or are not aware of current guidelines. **OBJECTIVES** To examine physician- and patient-based interventions designed to decrease overscreening and overtreatment by increasing adherence to US guidelines for women under 30 years of age. Specifically, the interventions will focus on increasing average intervals between screening and decreasing the number of excisional procedures. The long-term objective is to identify effective strategies to increase adherence to screening guidelines nationwide. **METHODS** We will conduct a randomized intervention clinic with two arms and use Family PACT administrative data for sampling, baseline, and outcome assessment. We will select 14 clinics from the Family PACT provider network that evaluate at least 200 female clients under 30 years of age per year. Clinics will be randomized to 1 of 2 arms: 1) mobile application (APP)-based intervention for providers, and 2) APP-based intervention for providers plus patient-centered approach (PCA) intervention. These groups will be compared to a comparison group of 7 clinics chosen at random (those not randomized). The APP intervention is for clinicians' mobile phones and will maneuver them through current guidelines based on age and condition. The PCA intervention will be patients' education using a tablet at the time of check-in to assist in understanding guidelines, asking questions of their providers, and assist them in evaluating treatment options. Family PACT serves predominantly uninsured women and 40% of clients are Latina. Development of the interventions will be conducted with input from all stakeholders including women from the community who are members of the National Cervical Cancer Coalition, and the Latina Contra Cancer, the American Congress of Obstetricians and Gynecologists, the State Office of Family Planning, the American Society for Colposcopy and Cervical Pathology and Quest laboratories. We plan to enroll 7 sites into each intervention arm with an average of 2800 to 3500 women aged 21-29 years per arm with a similar number of sites and women randomly chosen for the comparison arm resulting in a total of 21 sites and 8400-10500 women. Outcomes will be compared between study arms using t-test adjusting for clustering by clinic. **PATIENT OUTCOMES** We will use Family PACT claims data to calculate for each clinic by age, the number of and average interval between cytology specimens, colposcopy examinations and the number of excisional procedures. **SIGNIFICANCE** We will define successful interventions that will reduce unnecessary screening and treatment for cervical cancer screening in young women.

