## **Study Implementation Procedures**

### *Study Enrollment Procedures*

#### Contacting sites:

A letter will be sent to all clinic administrators of eligible sites explaining the study. A follow-up phone call will occur one week later. We will explain the study over the phone and those interested and agree to participate will be identified as clinics eligible to randomize to an intervention arm. If more than 14 sites agree to participate, we will let the sites know that they may not be asked to participate. If more than 14 sites agree, the 14 sites will be chosen based on identifying a balance of private and public clinics so that the average number of women aged 21-29 years is 500, and a relative geographic distribution among the 10 counties and that both English and Spanish languages are well represented according to the county's proportion of Hispanics.

Of those eligible for the comparison sites, we will identify sites using the eligibility criteria, and randomly identify 7 sites but with matching for private and public clinics and relative size of

practice which may range from 200 to over 1000 clients. There will be no contact with these sites since the outcomes data will be monitored from the Family PACT claims database.

Randomization:

Block randomization of clinics to one of the two arms will be performed by the biostatistical group at UCLA.

Site set up:

[name] and the PC will visit all 14 identified clinics sites to meet with staff, identify a key contact person for the site, discuss flow issues, and discuss the protocol.

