The primary outcome measure will compare the observed within-clinic changes in cervical cytology testing rates between intervention and comparison groups using a t-test accounting for clinic-level clustering. We will use the same approach to test differences between each of the APP and APP + PCA and the comparison groups. Tests will be adjusted for multiple comparisons. Secondary endpoints include examining the interval between tests for women who received two cervical cytology tests from the same provider and the decrease in the number (and percent) of women receiving colposcopy procedures and LEEP or cryotherapy procedures. These will be analyzed using a similar approach as adopted for the primary endpoint. Patient satisfaction surveys will be administered to all women evaluated and compared between interventions and the controls. Because most available data is on the clinic level, we will have limited opportunities to analyze patient-level data. However we will be able to conduct supplementary analyses to investigate the possible impacts of between-arm imbalances in clinic level characteristics such as racial/ethnic composition, age distribution, descriptors of lab procedures, additional app or educational materials that are not part of the assigned intervention, and cervical cancer screening educational activities. Prior to starting the intervention and during the study, administrators and physicians at each clinic site will be asked about possible confounding variables at their clinic.

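### The 90% power figure for the cytology rate makes no allowance for unequal clinic sizes, and the plan does not say how clinics are weighted

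*Combined protocol and SAP*

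**What the plan says.** Sample Size Estimates and Power Calculations bases the primary calculation on "3010 per arm, seven clinics per arm, and an average of 430 women per clinic". It assumes a "quite conservative value for the intracluster correlation of outcomes within clinics of 0.07", a control rate of about 50% that does not change, and a calculation that "is based on a 1% significance level to account for the fact that there will be two pairwise comparisons". On these inputs the design "will be sufficient to provide 90% power to detect a between-arm difference as small as 16% as significant". No CV of clinic size appears. The compared quantity is the change from baseline in each clinic's three-month rate, but no baseline-to-follow-up correlation is given. The gain from pairing is described as additional to the stated power.

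Elsewhere the plan expects clinics to differ in size. The inclusion criteria set a minimum of 200 women aged 21–29 in a fiscal year for intervention and comparison sites alike. Under Contacting sites, comparison clinics are matched on the relative size of "practice which may range from 200 to over 1000 clients", and the target average is 500 if more than 14 sites volunteer. The mean at eligible clinics is given as 560.

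On the test, Data Analyses compares within-clinic changes in rate "using a t-test accounting for clinic-level clustering". The Project Summary says "Outcomes will be compared between study arms using t-test adjusting for clustering by clinic". Neither states the weight that a clinic receives. Under Data Analyses, the rate's denominator is the women aged 21–29 in a quarter.

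**The concern.** An average cluster size and an ICC give the design effect for clusters of equal size. With unequal clusters the variance is larger, and how much larger depends on the weighting. If clinics are weighted by their number of women, the between-clinic part grows by about 1 + CV², and with seven clinics per arm one large site can carry a third of the arm. If clinics are weighted equally, small clinics with noisy rates count as much as large ones, and this costs more as the quarterly denominators shrink. In either case the power at the planned enrolment is below the equal-size figure.

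The open weighting matters separately. Each contrast has 14 clinics, and weighting by clinic or by woman can give different estimates. A choice left until the data are seen is avoidable analytic freedom on the primary endpoint.

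**Working it through.** **Inputs from the documents.** 7 clinics per arm; mean 430; ICC 0.07; rates 50% and 34% (the 16% read as percentage points); 1% significance level. Sidedness is not stated, so two-sided is assumed.

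**Inputs assumed.** The sizes within an arm, with the same pattern in both arms because comparison sites are matched on relative size; and the fraction of annual women seen in a quarter. All illustrative arms sum to 3010.

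**Step 1: the stated 90%, equal clinics, unpaired.** Variance of a clinic rate = p(1−p)[0.07 + 0.93/430].
- Control: 0.25 × 0.07216 = 0.01804. Intervention: 0.2244 × 0.07216 = 0.01619.
- SE of the difference = √[(0.01804 + 0.01619)/7] = 0.0699.
- Noncentral t, 12 df, noncentrality 0.16/0.0699 = 2.29: power **27.6%**.

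A normal approximation with effective n = 3010/[1 + 429 × 0.07] = 3010/31.03 = 97 per arm gives 39%. At 1% one-sided the t calculation gives 38.5%, and at 5% two-sided 55.7%. None reaches 90%.

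If changes are analysed and baseline and follow-up clinic rates correlate at r, the SE is multiplied by √[2(1−r)]. The SE that gives 90% is 0.0355, so 2(1−r) = (0.0355/0.0699)² = 0.258 and r is about **0.87**. The documents state no such value.

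**Step 2: unequal clinics on the printed inputs.** Each arm's variance is Σwᵢ²vᵢ, with vᵢ = p(1−p)[0.07 + 0.93/mᵢ].

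| Arm | CV | Women-weighted | Equal weights |
|---|---|---|---|
| 200, 250, 300, 400, 500, 600, 760 | 0.44 | 22.5% | 27.4% |
| 200, 250, 300, 350, 400, 500, 1010 | 0.59 | 19.5% | 27.3% |

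**Step 3: accept the 90% for equal clinics of 430, then vary the sizes.** With SE 0.0355 and between-clinic variance of change τ² equal in both arms, 7 × SE² = 2τ² + (b₀ + b₁)/m. Here b₀ = 2 × 0.25 = 0.50 and b₁ = 0.25 + 0.2244 = 0.4744.
- 7 × 0.001263 = 0.00884, and 0.9744/430 = 0.00227.
- τ² = (0.00884 − 0.00227)/2 = 0.00329, so τ = 5.7 percentage points.

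The 430 may be an annual count: the floor of 200 is defined on a fiscal year, whereas the endpoint uses a quarter. So τ was re-solved with the denominators cut to 50% and 35%, giving τ = 4.6 and 3.4 points, each time keeping 90% for equal clinics. Each arm's variance is then Σwᵢ²(τ² + b/mᵢ). Power, women-weighted / equal / inverse-variance:

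| CV | Full denominator | 50% | 35% |
|---|---|---|---|
| 0.20 (300 to 570) | 89.0 / 89.6 / 89.7 | 89.3 / 89.3 / 89.7 | 89.6 / 88.9 / 89.7 |
| 0.44 | 85.1 / 88.1 / 88.7 | 86.8 / 86.1 / 88.3 | 88.3 / 84.4 / 88.7 |
| 0.59 | 80.8 / 87.6 / 88.2 | 84.0 / 85.2 / 87.5 | 86.8 / 83.0 / 87.9 |

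Every entry is below 90%. At the full denominator equal weights beat women-weighting; at 35% the order reverses for all three arms. For scale, seven clinics averaging 430 that include both a 200 and a 1000 have a CV of at least 0.56, reached when the other five are 362 each.

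**The case against.** The plan nowhere says that it weights by women. A comparison of clinic-specific changes reads more naturally as one value per clinic, and Data Analyses adds that most of the data are at clinic level. A reader might infer from the clustering adjustment, and from a size expressed in women, that women are pooled, and so report a specific loss of power that equal weights would repair. The documents do not support that. The wording is compatible with either weighting, and Step 3 shows that the advantage of equal weights depends on the quarterly denominators and can reverse.

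Nor can one say that each arm will span 200 to over 1000. That range is given for selecting comparison practices, is stated as a possibility, and counts clients rather than women aged 21–29. Carrying it over to the intervention arms is an inference from the size matching. With a narrow spread the loss is about 1 point.

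The planned leave-one-clinic-out analysis would show dependence on a single large clinic, though it does not restore power. Finally, the gap between 28% and 90% is far larger than any effect of clinic size, so size variation is second-order. All of this stands. It limits the point to a power statement that omits an expected feature of the design, and a weighting rule that is missing.

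**Conclusion.** The point holds in this limited form: the stated 90% applies at best to equal clinics, the plan expects unequal ones, and the weighting is unspecified. Taking the 90% as given, the loss is about 1 point at a CV near 0.2. At CVs of 0.44 to 0.59 it is about 1 to 9 points, depending on the weighting and the quarterly denominator; inverse-variance weights lose least, at 1 to 2.5 points. On the printed inputs, unpaired, power is about 28% with equal clinics and 19.5–27% with unequal ones, so the 90% cannot be accepted without a stated correlation.

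The size rests on assumed clinic sizes, assumed quarterly fractions, a two-sided 1% level and a common between-clinic variance in both arms. That no size variation, correlation or weighting is stated does not rest on any assumption.

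**What to change.** In Sample Size Estimates and Power Calculations, recompute and restate the power using (a) the CV of clinic size from the Family PACT counts already held, (b) the quarterly denominators that the endpoint uses, (c) an explicit correlation between baseline and follow-up clinic rates, and (d) the weighting actually planned.

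In Data Analyses, and in the matching sentence of the Project Summary, state that each clinic contributes one within-clinic change and name the weighting in advance, either equal or inverse-variance. Apply the same rule to the APP versus APP+PCA contrast, and report the woman-weighted result as a sensitivity analysis.

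The cost is one recalculation and some wording; no new sites or data are needed. There are three drawbacks. The stated power will be less favourable. Equal weights estimate the effect in the average clinic rather than for the average woman, which the sensitivity analysis covers. Inverse-variance weights require a between-clinic variance estimated from only seven clinics per arm, so the method for estimating it should be fixed beforehand.
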